2) Exclusion Criteria

- Multifocality (≥ 3)
- Residual diffuse microcalcification
- Patients who drop out due to complications or cancer progression during neoadjuvant chemotherapy.
- Patients with residual tumors observed immediately before surgery, as observed by MRI and ultrasound.

3) Target number of patients and basis of calculation

The primary endpoint of this study is to perform an additional biopsy after MRI to determine if specificity was greater than 90% (one-sided test). To calculate the number of patients to meet this primary endpoint, the following assumptions were made.

※ Gold standard: biopsy after surgery

- (1) Level of significance, $\alpha = 0.05$, one-sided test
- (2) Type II error (β) is 0.20, and the test power is maintained at 80%.
- (3) The hypothesis of this study is as follows.

Null hypothesis: The specificity of MRI + biopsy is not 64% ($p \neq 0.64$).

Alternative hypothesis: The specificity of MRI + biopsy is greater than 64% ($p > 0.64$). However, a specificity of 90% is expected.

(4) Based on the results from previous studies, MRI data showed that 64% of the patients had no tumors in the actual surgical tissues. Therefore, the specificity of MRI is assumed to be 64%. In case of MRI + biopsy, specificity is expected to be 90%.

Based on this, the number of study patients was calculated using the below formula.

$$n = \frac{(z_\alpha \sqrt{p_0 q_0} + z_\beta \sqrt{p_1 q_1})^2}{\delta^2}$$

Based on the calculation, 17 patients are required to secure 80% probability of rejecting the above null hypothesis at a significance level of 5%.

At this time, 17 patients were counted using the specificity (ratio of complete response in the MRI + needle biopsy results from the patients who would show complete response in the biopsy after surgery [gold standard] results), so it would only represent the number of patients who would have complete response as a result of biopsy after surgery. Therefore, the total number of patients should be calculated by reflecting prevalence (among 100 patients suspected of complete response in our study, the ratio of actual complete response in the postoperative biopsy is 64%) and the results are as follows.

Prevalence (A)	Total number of patients (B)	Number of total study patients considering the dropout rate 10% (C)
64%	27	30

4) Study Patient Recruitment Plan

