Based on the above calculations, a total of 30 patients would be sufficient for this study. However, an additional 10 patients were included for further analysis to compare multiple-core needle biopsy and vacuum-assisted breast biopsy, thereby allowing 20 patients in each group.

Among the patients who were admitted for surgery after neoadjuvant chemotherapy (admitted 2 days before surgery), those who were expected to have a complete response immediately before surgery, based on the MRI and ultrasound results, will be given an explanation with regard to study plan, etc.

5. Study Method

1) Detailed study method

A. Breast MRI for assessing response after neoadjuvant chemotherapy

- Breast MRI diagnosis will be interpreted independently of clinical measurements, mammography, and breast ultrasonography results.
- Two breast MRIs will be done for patients who have received neoadjuvant chemotherapy, one before and one after the therapy.
- The images obtained before and after chemotherapy will be examined by a breast diagnostic imaging specialist to assess the exact response of the tumor to neoadjuvant chemotherapy and the presence of residual tumor.
- A complete MRI response means no abnormal contrast enhancement, no mass, or no distortion of the breast tissue in all phases of the MRI and in all compartments of the breast.
- A near complete MRI response means tumor size ≤ 0.5 cm or Lesion-to-Background Signal Enhancement Ratio [L-to-B SER] ≤ 1.6 .
- The response will be evaluated based on the results of breast ultrasonography and mammography, in addition to breast MRI. In case of residual tumor findings, such as clustered microcalcification on mammography, the patient will be excluded even when an abnormal contrast enhancement is not observed.

B. Biopsy in patients whose complete response is predicted by breast MRI

- In previous studies, attempts to predict the complete response using diagnostic images of breast alone showed about 21% false negative findings. Additional confirmation of pCR using multiple-core needle biopsy or vacuum-assisted breast biopsy can lower such false negative findings.
- A needle biopsy or vacuum-assisted breast biopsy will be performed around the residual tumor and the periphery and a wire will be inserted for localization of the biopsied area. The wire will guided the subsequent wide excision.

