4. Reporting procedures to the IRB, sponsor and, where applicable, the regulatory agency (description on the reporting method and period to the IRB, sponsor, or regulatory on adverse events, unexpected problems, non-compliance with the protocol, etc.)

: Problems encountered during the study will be discussed with the principal investigator, [name] and will also be reported to the IRB office.

9) Data Analysis and Statistical Analysis Method

The results from the preoperative MRI and biopsies (multiple-core needle biopsy and vacuum-assisted breast biopsy) and postoperative pathology will be compared to examine the accuracy of the prediction of complete response or residual tumor.

Primary Endpoint

- Negative-predictive value (NPV)

Secondary Endpoint

- False negative rate (FNR)
- Accuracy
- NPV, FNR, and accuracy analysis for cases meeting all the conditions of MRI size ≤ 0.5 cm, L-to-B SER ≤ 1.6 , and removal of multiple-core needle biopsy 5 core or more

In addition, the patients will be divided equally into the multiple-core needle biopsy group and the vacuum-assisted breast biopsy group to determine which biopsy method could predict the complete response more accurately.

6. Measures for the Protection of Patients

1) Basic measures for securing research ethics

This study will be initiated after receiving IRB approval and conducted in compliance with the 2013 Helsinki Declaration and ICH-GCP

2) Measures to protect personal information of patients

Patients' information, collected for study purpose, will be stored in the laboratory as password-protected files. Access to these files will be restricted to the principal investigator and co-investigators. Personally identifiable information, acquired during data collection, will not be recorded. Especially, patient's name, national resident number, and hospital registration number will not be documented in the case record.

When the results of the study are published, no identification data of the patients will be provided and the case records will be kept separately with the principal investigator, until the final publication of the results after study termination. The data and records will be retained for three years after the termination of the study. Subsequently, these will be discarded under the direction of the principal investigator in accordance with the Article 16 of the Enforcement Decree of the Personal Information Protection Act.

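### Section 4.3) states the primary aim as showing specificity above 90%, but its hypotheses, sample size and 80% power are for exceeding 64%, and the null is miswritten

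*Combined protocol and SAP*

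**What the plan says.** Section 4.3) (target number of patients) opens by describing the primary objective as adding a biopsy after MRI "to determine if specificity was greater than 90% (one-sided test"), and says the patient number was calculated to meet it. The hypotheses that follow use another value:

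- "Null hypothesis: The specificity of MRI + biopsy is not 64"%, with the symbol p ≠ 0.64.
- The alternative is "The specificity of MRI + biopsy is greater than 64"%, followed by "However, a specificity of 90% is expected".

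Item (4) sets 64% as the MRI value and 90% as the value expected for MRI plus biopsy. The section then concludes that "17 patients are required to secure 80% probability of rejecting the above null hypothesis at a significance level of 5"%. It converts 17 to 27 using a 64% pCR prevalence, and to 30 using 10% dropout. Section 4.4) states that "a total of 30 patients would be sufficient for this study" and adds 10 patients to compare the two biopsy methods, making 40.

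The analysis section, 5.9), says only that the preoperative and postoperative findings "will be compared to examine the accuracy of the prediction of complete response or residual tumor". It names "Negative-predictive value (NPV") as the primary endpoint and gives no threshold, test or interval.

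**The concern.** One primary test has two stated success thresholds, 90% in the aim and 64% in the hypotheses, and the power statement covers only the second. The null as written makes this worse. A null of p ≠ 0.64 includes every value the alternative is meant to establish and excludes the value used in the formula. Rejecting it literally would mean concluding that specificity equals 64%.

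What is at stake is an overstated performance claim. A significant test supports specificity above 64%, but an estimate slightly above 90% could be presented as having met the written aim. The two criteria can also disagree on the same data: 15/17 (88.2%) is significant against 64% yet below 90% even as an estimate.

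The limits of the point should be clear. Specificity errors here are tumour-free patients with a positive biopsy, so this is not a count of missed tumours. No treatment within the trial depends on the result.

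**Working it through.** **Inputs**, all from sections 4.3) and 4.4): one-sided α = 0.05; power 80%; p0 = 0.64; p1 = 0.90; pCR prevalence 64%; dropout 10%; enrolment 40.

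**1. Reproducing the plan's figures.** With the protocol's formula,

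n = (1.645·√(0.64·0.36) + 0.842·√(0.90·0.10))² / 0.26² = 16.06, rounded up to 17.

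Then 17/0.64 = 26.6, rounded up to 27, and 27/0.9 = 30. The arithmetic is right, and it is a design against 64%. A two-sided 5% level would give 21.06, so 22.

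**2. The aim as written.** With H0: p ≤ 0.90, the value the plan expects (90%) lies on the boundary of the null. A valid 5% test then has at most 5% power at any sample size; in the formula the difference p1 − p0 is zero. With 17 pCR patients even 17/17 gives p = 0.9^17 = 0.167. Rejection first becomes possible at 29/29 (0.9^29 = 0.047).

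**3. Likely numbers of pCR patients.** These are 17 (the plan's requirement), 23 (36 evaluable after 10% dropout; 36 × 0.64 = 23.0), and 25 or 26 (40 × 0.64 = 25.6).

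**4. What each criterion delivers.** Lower bounds are exact (Clopper-Pearson) one-sided 95%. With no errors the bound is 0.05^(1/n).

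| pCR patients | Smallest estimate above 90% | Its lower bound | Lower bound with no errors | Chance of estimate >90% at true 90% | Same at true 85% |
|---|---|---|---|---|---|
| 17 | 16/17 = 94.1% | 75.0% | 83.8% | 48% | 25% |
| 23 | 21/23 = 91.3% | 75.1% | 87.8% | 59% | 31% |
| 25 | 23/25 = 92.0% | 76.9% | 88.7% | 54% | 25% |
| 26 | 24/26 = 92.3% | 77.7% | 89.1% | 51% | 23% |

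The no-error bound first passes 90% at 29 patients (90.2%). The last two columns apply only if an estimate above 90% is taken as showing specificity above 90%. That claim would then be made about half the time when the truth is exactly 90%, rather than at most 5% of the time.

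**5. The test against 64%.** The protocol names no test; these figures assume an exact binomial test at one-sided 5%.

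| pCR patients | Cut-off | Actual size | Power at true 90% |
|---|---|---|---|
| 17 | 15/17 | 0.027 | 76% |
| 23 | 19/23 | 0.045 | 93% |
| 25 | 21/25 | 0.025 | 90% |
| 26 | 22/26 | 0.019 | 89% |

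A score test has the same 15/17 cut-off at n = 17. The number of pCR patients is itself random. Averaged over Binomial(N, 0.64), exact power is 75% with 27 evaluable patients, 88% with 36 and 91% with 40.

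**The case against.** The strongest reply is that this is loose wording in one opening sentence of a translated protocol. Section 4.3) has one formula and one sample size, says twice that 90% is the expected value, and reproduces exactly on that reading. No passage says that an estimate above 90% counts as success, so the misuse probabilities describe a rule the plan does not state. This stands in part: a test against 64% is the natural reading, and those probabilities are conditional. But the text does present 90% as the value to exceed. Section 2, item 2)A, calls 90% or higher acceptable (for accuracy), so a reader could take 90% as a real target, and section 5.9) does not rule that out.

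A second reply is that 90% may be the true target, so the choice between thresholds should be the sponsor's. The sponsor may choose it, but the present calculation cannot support it: at an expected 90% no sample size powers a test of more than 90%. A higher true value would have to be assumed. At 95%, for example, the same formula gives 184 pCR patients, or 288 in total and 320 with dropout.

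A third reply is that 64% is a doubtful benchmark, because it comes from the pCR rate among patients with an MRI complete response, and that section 5.9) names NPV as primary and does not list specificity. Both are fair and need their own resolution. Neither removes the contradiction within 4.3), but they limit how far the power figures reassure.

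**Conclusion.** The point holds. As written, the stated aim (above 90%) is not what the design tests (above 64%), the 80% power does not apply to that aim, and the null hypothesis is invalid. A positive primary test would support only specificity above 64%. At the expected pCR counts of 17 to 26, no result, not even one without errors, places the exact one-sided 95% lower bound above 90%; the best attainable is 83.8% to 89.1%.

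This rests on the plan's own 64% prevalence and 10% dropout, and on exact binomial methods, which the plan does not specify. The pCR count could exceed expectation, but 29 or more would still have to be classified without error at the 29-patient minimum. The sample-size arithmetic is correct for the 64% null; the fault is in the stated aim and the stated null. It should be fixed, since it governs what may be claimed, although it does not affect patients' treatment in the trial.

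**What to change.** In section 4.3):

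- State the hypotheses as *H0: specificity ≤ 0.64; H1: specificity > 0.64 (one-sided 5%)*.
- Restate the aim as *to show that specificity exceeds 64%, with 90% assumed for power*.
- If the exact binomial test is used, give its power at a true 90%: 76% with 17 pCR patients, 93% with 23, 90% with 25 and 89% with 26. The planned 40 therefore suffices for this test, whereas 30 enrolled (27 evaluable) would give about 75%.
- State that 17/27/30 holds only while specificity is the tested measure, because the 17 are pCR patients. NPV has biopsy-negative patients as its denominator, and its status as primary endpoint in 5.9) must be reconciled separately.

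In section 5.9), add: *Specificity is reported with its exact (Clopper-Pearson) confidence interval. An estimate above 90% is not described as having shown specificity above 90% unless the one-sided 95% lower bound exceeds 90%.*

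The cost is wording in two sections. Enrolment, data collection and procedures are unchanged while specificity is the measure tested. The drawback is a less favourable permitted claim: a statement of more than 90% is out of reach at the expected pCR counts.

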 - In a previous study, sensitivity to residual tumors after neoadjuvant chemotherapy was measured using breast MRI was at 83%, specificity 47%, positive-predictive value (PPV) 47%, negative-predictive value (NPV) 83%, and accuracy 74%.
 - Histological examination of tumors is considered to be an important factor in improving accuracy. The accuracy of pCR prediction is determined to be acceptable when it is 90% or higher, considering that local recurrence rate is about 10% in patients undergoing surgical resection, as observed in previous studies.
 - In this study, pCR prediction results of breast magnetic resonance imaging (MRI) and biopsy (multiple-core needle biopsy and vacuum-assisted breast biopsy) will be compared with the prediction results of the breast specimens undergoing quadrantectomy involving primary tumors.
 - If residual tumors are observed in the surgical specimens, pathological factors such as the distance from the primary tumor with clipping and the occurrence of necrosis will be analyzed.
- B. To develop a basic examination technique that would allow screening of patients based on whether they need local resection or not, when making preoperative determination by pathological response.
 - The pCR after neoadjuvant chemotherapy will be determined by non-surgical method.
 - Using a RCT design, enrolled patients will be divided into two groups based on whether they received

- surgery or not.
- Follow-up with local recurrence rate will be the primary endpoint, while disease-free survival (DFS) and overall survival (OS) will be the secondary endpoints. Based on the results, patients who do not need surgical treatment will be identified.
- In this study, if the pCR can be accurately determined, it is possible to conduct further studies on the extent of surgery (local excisional biopsy with local anesthesia vs. multiple-core needle biopsy vs. segmentectomy)

3. Investigational product and medical device code name (or common name of main ingredient), amount of drug substance, formulation, etc. (including a control drug)

Not applicable.

4. Selection Criteria, Exclusion Criteria, Target Number of Patients and Basis for Calculation

1) Selection Criteria

All patients undergoing neoadjuvant chemotherapy and those who are expected to have near complete or complete clinical response immediately before surgery, as confirmed by MRI will be included. (tumor size ≤ 0.5 cm or Lesion-to-Background Signal Enhancement Ratio [L-to-B SER] ≤ 1.6).

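### Exceeding a fixed historical 64% cannot show that biopsy adds to MRI, and the plan has no comparison with MRI alone in its own cohort

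*Combined protocol and SAP*

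**What the plan says.** Section 4, 3) states the primary aim as "to determine if specificity was greater than 90% (one-sided test"), but sets the alternative hypothesis as "The specificity of MRI + biopsy is greater than 64" per cent. On the expected result it says: "In case of MRI + biopsy, specificity is expected to be 90" per cent. The sample size is meant to give 80% probability of "rejecting the above null hypothesis at a significance level of 5" per cent.

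The same section takes the 64% from earlier MRI data, as the share of patients with no tumour at surgery. It then reuses the figure as the pCR prevalence "among 100 patients suspected of complete response in our study".

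Other imaging figures appear elsewhere. Section 2, 2) A cites a previous MRI study with sensitivity 83%, specificity 47%, PPV 47%, "negative-predictive value (NPV) 83%, and accuracy 74" per cent; it also calls accuracy of at least 90% acceptable. Section 5, 1) B says that breast imaging alone "showed about 21% false negative findings", and gives a prediction rate of about 45% for luminal subtypes.

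Section 5, 9) names NPV as the primary endpoint, with no null value, threshold or test. Enrolment is limited to MRI near-complete or complete responders (section 4, 1)), and wide excision follows the biopsy (Study Overview). There is no MRI-only group and no planned comparison of MRI + biopsy with MRI alone.

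**The concern.** Section 5, 6) presents the study as raising predictive accuracy by adding biopsy to imaging. That is an added-value claim, so the comparator should be what MRI alone achieves in the same patients. A constant from an earlier series stands in for it. If this cohort has a higher pCR rate than that series, the difference is credited to biopsy. Section 5, 1) B itself reports that response and MRI prediction vary by subtype, so a shift in case mix is plausible. The result is intended to support omitting surgery, so a false claim of added value matters.

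**Working it through.** Residual tumour is the positive state. Specificity is the share of pCR patients called complete response; NPV is the share of those called complete response who have pCR.

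**1. The plan's own figure.** Inputs from section 4, 3): p0 = 0.64, p1 = 0.90, one-sided alpha 0.05, power 80%, dropout 10%.

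n = (1.645 × √(0.64 × 0.36) + 0.842 × √(0.90 × 0.10))² / 0.26² = (0.790 + 0.252)² / 0.0676 = 16.06, so 17. Then 17 / 0.64 = 26.6, so 27, and 27 / 0.9 = 30. The stated 17, 27 and 30 reproduce. Section 4, 4) raises enrolment to 40 to compare the two biopsy methods.

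**2. Specificity scale, as labelled.** The denominator is the pCR patients. A biopsy that is always negative scores 17/17 = 100% and rejects 64% every time, whatever the pCR rate.

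**3. NPV scale, as the 64% is described and as section 5, 9) makes primary.** The plan states no NPV null, so testing NPV against 0.64 is an assumption made here. With an always-negative biopsy, every evaluable patient is in the denominator and NPV equals the cohort's pCR rate. The exact rule is the smallest r with P(X ≥ r | n, 0.64) ≤ 0.05: 29 of 36 (40 less 10%) or 31 of 40. Probability that this biopsy passes:

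| True pCR rate | 36 evaluable | 40 evaluable |
|---|---|---|
| 64% | 2.5% | 5.0% |
| 70% | 11% | 20% |
| 73% | 20% | 33% |
| 79% | 51% | 68% |
| 83% | 74% | 87% |

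If the 64% is 64/100 (an assumption), its exact 95% interval is 54% to 73%. The 70% row therefore lies within the benchmark's own uncertainty, and 73% is its upper limit.

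**4. How firm the 79% and 83% are.**
- For the study in section 2, 2) A, PPV 47% with sensitivity 83% and specificity 47% implies residual-tumour prevalence 0.47 / (0.83 + 0.47) = 0.36. NPV is then 83%, but accuracy is 0.83 × 0.36 + 0.47 × 0.64 = 0.60, not 0.74.
- Accuracy 74% instead implies prevalence (0.74 − 0.47) / (0.83 − 0.47) = 0.75. NPV is then 0.47 × 0.25 / (0.47 × 0.25 + 0.17 × 0.75) = 0.48. The five figures do not cohere, so NPV may be 83% or about 48%.
- The 79% is 100% − 21%. It is an NPV only if the 21% is a share of predicted responders; the protocol gives no denominator, and the figure concerns breast imaging, not MRI specifically.
- At true rates of 45% to 48% the useless biopsy passes less than 0.1% of the time at 36 or 40 evaluable.

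**5. If an observed value of at least 90% were required.** The rule is 33 of 36 or 36 of 40. The always-negative biopsy passes 3.9% and 5.7% of the time at 79%, and 11.7% and 16.7% at 83%.

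**6. The within-cohort alternative.** One-sided Fisher exact test of biopsy result by pCR status, 36 evaluable, by full enumeration. Sensitivities and specificities are assumed.
- Uninformative biopsy: it rejects 1.3–1.6% of the time (sensitivity 0.1, specificity 0.9), 2.0–2.2% (0.2, 0.8) and at most 2.4% (0.5, 0.5).
- Informative biopsy, specificity 90%, at pCR rates of 64%, 79% and 83%: power 99%, 95%, 90% if sensitivity is 80%, and 74%, 60%, 52% if it is 50%.

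**The case against.** A fixed historical benchmark is common in a 40-patient accuracy study. The 64% comes from patients suspected of complete response, so it is the figure best matched to the enrolled population. All patients have surgery, so the cohort's pCR proportion will be visible in any report. The protocol also names 90%, a much harder bar.

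Much of this stands. A reader might infer that the protocol's MRI-alone figures run from 64% to 83% and that the false-claim rate is therefore 51% to 87%. The documents do not support that: the only previous-study MRI specificity is 47%, the luminal rate is about 45%, and the upper values rest on figures that do not cohere or lack a denominator. Nor do the documents establish that 64% alone decides success, because 90% is also named.

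What does not stand is that these points cure the problem. The protocol never says which bar decides. The 90% bar also lacks an MRI-alone comparator. Being able to read off the pCR proportion afterwards is not a planned comparison.

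**Conclusion.** The concern holds in a limited form. As written, exceeding 64% is not evidence that biopsy improves on MRI. On the specificity scale the test cannot fail a biopsy that never finds tumour. On the NPV scale, false success is 11–20% at a true pCR rate of 70% and 20–33% at 73%, against a nominal 5%. This assumes an NPV null of 64%, 36 to 40 evaluable patients and, for the 73%, that the benchmark is 64/100. The 51–87% at 79–83% is conditional on doubtful readings. Below 64% false success is rare, and a 90% rule would hold it to about 4–17% at 79–83%.

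The underlying fault is that an NPV is used as a specificity null while the endpoint section names NPV and no criterion. Confidence is medium, because the documents fix neither the deciding bar nor the true MRI-alone value.

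**What to change.** In section 5, 9), state NPV as the one primary measure and bring the hypothesis in section 4, 3) into line with it. Report the cohort's MRI-alone NPV (pCR among all evaluable patients, exact CI) beside the NPV among biopsy-negative patients (exact CI). Base any claim that biopsy adds to MRI on the within-cohort 2x2 table, for example by a one-sided Fisher exact test. Judge adequacy separately against the 90% bar, because a significant Fisher test shows only association: at 64% pCR, a biopsy with sensitivity 50% and specificity 90% has NPV 0.576 / (0.576 + 0.18) = 76%, yet is significant 74% of the time. Keep 64% as historical context.

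The cost is one extra analysis of data already collected. The downsides are that beating 64% alone no longer counts as success, and that power for the added-value claim is modest (52–74% at 36 evaluable) if biopsy sensitivity is only about 50%.

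### The 80% power stated for 17 pCR patients is 76% once counts are whole numbers, and whether 30 enrolled patients suffice depends on a test the protocol does not name

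*Combined protocol and SAP*

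**What the plan says.** Section 4, item 3 (target number of patients) sets a one-sided 5% level and states that "Type II error (β) is 0.20, and the test power is maintained at 80" per cent. For the null value, "the specificity of MRI is assumed to be 64" per cent; for the alternative, "In case of MRI + biopsy, specificity is expected to be 90" per cent. The text says that "the number of study patients was calculated using the below formula", and the displayed formula is the one-sample normal approximation for a proportion. Its conclusion is that "17 patients are required to secure 80% probability of rejecting the above null hypothesis at a significance level of 5" per cent.

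The section explains that these 17 are only the patients who turn out to have pCR at surgery, so "the total number of patients should be calculated by reflecting prevalence". With 64% prevalence this gives 27 patients, and with 10% dropout 30. Section 4, item 4 then says that "a total of 30 patients would be sufficient for this study" and adds 10 patients so that the two biopsy methods can be compared with 20 each. Planned enrolment is therefore 40.

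Neither Section 4 nor the analysis section (Section 5, item 9) names the test for the specificity hypothesis. Section 5, item 9 lists NPV as the primary endpoint.

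**The concern.** The formula relies on a large-sample approximation, yet it is applied to 17 patients with an expected proportion of 0.90. At that size the number of correctly classified patients moves in steps of about 6 percentage points (1/17). A rule with exactly 5% error does not exist, and the real power can differ clearly from the formula's value.

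The step from 17 to 27 raises a second question. Dividing by 0.64 gives the number of patients at which 17 pCR cases are expected on average. The actual number is random and will often be lower.

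What is at stake is the accuracy of the stated justification. A reader who relies on it would take 17 pCR patients, or 30 enrolled, as securing 80% power at 5%.

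**Working it through.** **Inputs**, all from Section 4, item 3: p0 = 0.64; p1 = 0.90; one-sided alpha = 0.05 (z = 1.645); power 80% (z = 0.842); pCR prevalence 0.64; dropout 10%. The null hypothesis as printed says only that specificity differs from 64%. I take it as p = 0.64, which is what the formula uses.

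**1. The plan's own figures.**
- √(p0·q0) = √(0.64 × 0.36) = 0.48; √(p1·q1) = √(0.90 × 0.10) = 0.30; δ = 0.26.
- n = (1.645 × 0.48 + 0.842 × 0.30)² / 0.26² = (0.7895 + 0.2525)² / 0.0676 = 16.06, rounded up to 17.
- 17 / 0.64 = 26.6, rounded up to 27; 27 / 0.90 = 30.

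Every step reproduces. The same approximation gives power at n = 17 of Φ[(√17 × 0.26 − 1.645 × 0.48) / 0.30] = 82.7%.

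**2. True power at 17.** Let X be the number correctly classified among 17 pCR patients.
- P(X ≥ 14 | 0.64) = 8.9%, above 5%.
- P(X ≥ 15 | 0.64) = 2.7%, so the exact cut-off is 15 of 17.
- Score test: 14/17 gives z = (0.8235 − 0.64) / (0.48/√17) = 1.58, below 1.645; 15/17 gives z = 2.08. The cut-off is again 15 of 17.
- Power: P(X ≥ 15 | 0.90) = 0.280 + 0.315 + 0.167 = 76.2%.

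The result at 17 is therefore the same for both tests.

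**3. Neighbouring sizes, exact test.**

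| pCR patients | Reject at | True alpha | Power |
|---|---|---|---|
| 16 | ≥14 | 3.8% | 78.9% |
| 17 | ≥15 | 2.7% | 76.2% |
| 18 | ≥16 | 1.9% | 73.4% |
| 19 | ≥16 | 4.95% | 88.5% |
| 22 | ≥19 | 2.0% | 82.8% |

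Exact power stays above 80% for every size from 19 to 30; the lowest value in that range is the 82.8% at 22.

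**4. Random pCR count.** Let K, the number with pCR among N evaluable, be Binomial(N, 0.64). Then P(K ≥ 17 | N = 27) = 62.9%. Power is averaged over K, with the cut-off reset at each K:

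| Evaluable N | Exact test (5% held at each K) | Score test |
|---|---|---|
| 27 | 75.0% | 82.7% |
| 29 | 79.3% | 85.1% |
| 30 | 81.1% | 86.2% |
| 36 | 88.3% | 91.7% |
| 40 | 91.4% | 94.3% |

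At N = 27 the score test's alpha averages 4.6%. It exceeds 5% at some counts: 7.3% at K = 14, 5.3% at 15, 6.7% at 18 and 6.0% at 22. The chance that K falls on a count where it exceeds 5% is about 36%.

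If dropout is also random at 10%, exact power is 74.8% for 30 enrolled and 88.1% for 40 enrolled. The exact test first passes 80% at 30 evaluable; 30 / 0.90 = 33.3, so about 34 enrolled.

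**The case against.** The strongest reply is that nothing has been miscalculated. The formula is standard and openly shown, and 17, 27 and 30 all follow from it. The score test is the test that matches the formula. Averaged over the random pCR count, it gives 82.7% power at 27 evaluable with average alpha below 5%, so 30 enrolled is defensible on the plan's own method. Besides, 40 patients are planned.

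Much of this stands. A reader might infer that the chain is an arithmetic error, that 30 is plainly too few, or that only the 10 patients added for the device comparison bring the main test to 80%. The documents do not support the first inference. The other two hold only for an exact test held to 5% at every pCR count, which the protocol does not prescribe. Nor is the random count by itself the cause of the shortfall. The score test faces the same random count and passes 80%; the exact test falls short because whole-number cut-offs leave it conservative, with average alpha of 2.9% at 27 evaluable.

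Two things survive the reply. The sentence about 17 is untrue under either test. And the score test reaches 80% at 27 partly through counts at which it breaches the stated 5%, so the sufficiency of 30 cannot be confirmed until the test is named.

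**Conclusion.** The concern holds in a limited form. The stated 80% power at 17 pCR patients is really 76.2%, with true alpha 2.7%, under both the exact and the score test. Whether 27 evaluable (30 enrolled) reach 80% is open: 75.0% with the exact test, 82.7% with the score test.

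It would be tempting to conclude that the trial is underpowered for this hypothesis. On the plan's own assumptions it is not. The planned 40 give about 88% (exact) or 92% (score) power at 36 evaluable. The fault lies in the stated figures and the unnamed test, not in the size of the trial, and the documents contain no plan to stop at 30.

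These results assume a true specificity of 90%, a fixed comparator of 64%, 64% prevalence, 10% dropout, and both biopsy methods pooled. They say nothing about power for NPV, the primary endpoint listed in Section 5, item 9.

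**What to change.** Text changes in Section 4, items 3 and 4, and Section 5, item 9:

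- Name the one-sided exact binomial test for the specificity hypothesis.
- Replace the 80% at 17 with 76.2% (reject at 15 or more of 17, alpha 2.7%). Alternatively, give 19 as the size from which exact power stays above 80% through 30 (16 or more of 19, alpha 4.95%, power 88.5%).
- Keep the statement that 30 is sufficient only with a qualification: averaged over the pCR count, exact power is 75% at 27 evaluable and first passes 80% at 30 evaluable (81.1%), about 34 enrolled.
- State that the planned 40 give about 88% exact power at 36 evaluable.

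Take the 30 evaluable from the averaged power. Although 19 / 0.64 = 29.7 leads to the same number, it again treats the pCR count as fixed: the chance of at least 19 among 30 is only 61%.

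The cost is wording only, with no change to enrolment or conduct. If the sizing is reconciled with NPV as the primary endpoint, the calculation must be redone with the number of biopsy-negative patients as the random denominator.
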